## 5.6. Follow-up

All patients will be followed for the initial 72 hours following admission into ED by a clinician and then again chart reviewed at 30 days from initial admission.

## 6. Ethical and regulatory considerations

### 6.1 Ethical considerations

This study will take the form of a prospective cohort study. There will be no change to the management of patients, no advice or guidelines given to the data collectors/clinical team. The aim will be to collect information on the routine practice of different hospitals around AoNZ. There is no foreseen impact on standard patient care and therefore no risk to patients involved in this study. There will be no contact with patients and follow-up data will be collected from routine clinical notes; No phone calls will be made.

### 6.2 Ethical approval

HDEC approval will be applied for considering the prospective design of the study. Each participating centre will be required to apply for locality ethical or audit approval as appropriate to their centre.

### 6.3 Data handling and storage

Data will be collected and stored using the web application Research Electronic Data Capture (REDCap). It is encrypted with HIPAA-Security and compliant with guidelines in the United States and is widely used by academic institutions. Each collaborator will be given secure REDCap server login details, allowing secure data storage on the REDCap system. Collaborators will be unable to upload identifiable information to the REDCap database. All anonymous data will be held for a total of ten years, after which it will be permanently removed from the server space.

When creating an entry for a patient in REDCap a unique REDCap ID for each patient is created. Each collaborator will be asked to keep a spreadsheet on a password protected hospital computer to store NHI and the corresponding REDCap ID. This will give investigators the opportunity to use the data in the future if required. Data will only be stored for a period of 10-years after which it will be permanently deleted.

All centres will be required to have locality approval prior to starting data collection.

### 6.4 Transfers

In the event of patient transfer to another participating site, data collectors are required to inform the hospital lead at the transferring hospital. The hospital lead will then liaise with the hospital lead at the receiving site to ensure continuity of data collection. Each individual will only have one entry for a given episode of AP.

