## 5. Methods

### 5.1 Study Setting

PANORAMA welcomes the participation of any publicly funded secondary or tertiary hospital in AoNZ under the Te Whatu Ora Health NZ directorate. All centres intending to take part in the study must register in accordance with local regulations and proof of registration must be provided to ACTT before initiating the data collection process.

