### 5.3. Data Collection

An investigator at each contributing hospital will be appointed to be responsible for data collection of all appropriate patients. Patients for AP may be admitted under multiple teams, it is the hospital lead's responsibility to capture all patients with AP that occur during the study inclusion period.

Data will be collected and stored using the web application REDCap. This web application is encrypted with HIPAA-Security, compliant with guidelines in the United States, and is widely used by academic institutions.

REDCap is a secure, web-based software platform designed to support data capture for research studies. It provides: 1) an intuitive interface for validated data capture; 2) audit trails for tracking data manipulation and export procedures; 3) automated export procedures for seamless data downloads to common statistical packages; and 4) procedures for data integration and interoperability with external sources.

Clinical data at each participating hospital will only be accessed by medical students and resident medical officers who already have access to the clinical data being collected. Individuals working at other centres, and those without access to patient clinical data, will not be involved in data collection. Locality approval will be sought and obtained at all centres prior to study commencement. An excel spreadsheet will be kept alongside the REDCap database at each hospital. This will be stored on a password protected hospital computer at each hospital. A unique RedCap number will be created for each patient. This number will allow re-identification of patients by the local hospital lead if required. After data has been uploaded into REDCap the local hospital copy of the data will be destroyed to protect patient privacy. An excel spreadsheet containing the REDCap key and the relevant patients NHI will be kept. This excel spreadsheet will allow future patient re-identification if required. During REDCap data upload there will be no data fields where identifiable data can be uploaded; for example, names or NHI's. Local excel files will be stored at each hospital for 10 years and destroyed following this. The central de-identified data set will be stored for 10 years using REDCap electronic data capture tools.

If further studies using this data set are to be performed a subsequent ethics application will be required before its use.

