Type of opioid prescribed (if any)	Codeine/ Morphine/ Fentanyl/ Tramadol/ Oxycodone/ Other (please specify)/ no opioids prescribed
Date opioid analgesia first administered	Date (dd/mm/yyyy)
Time opioid medication is administered to patient	24 hour clock
Route	PO/ IV
(If regular) daily dose	mg
(If PRN) total dose in first 72 hours	mg

(If yes) Date opioids first administered	Date (dd/mm/yyyy)
(If yes) Time opioid medication first administered as per drug chart?	24 hour clock
Further analgesic modalities	PCA/ ketamine/ local nerve blocks/ other (please specify)
Transfer to different hospital	
Patients with predicted severe disease discussed with specialised pancreas service ( Appendix B ) in first 72 hours from admission	Yes/ No/ not applicable
Patient transferred to a different hospital in the first 72 hours?	Yes/No
(If yes) Date of transfer	Yes/No
(If yes) Location transferred to	List of hospitals
(If yes) Reason for transfer to different hospital?	Severe disease/ requires ERCP/ requires interventional management of local complication/ other (free text)
ERCP	
Cholangitis in first 72 hours ( Appendix F )	Yes/ No
Cholestasis in first 72 hours (radiological + deranged LFTs)	Yes/ No
ERCP performed in the first 72 hours	Yes/ No
Fluid management*	
Baseline variables	
Bag 1	
Date of administration	Date (dd/mm/yyyy)
Time of administration	Time (24-hour)
Volume administered	Volume (ml)
How long does fluid run for?	Time (hours)
Type of fluid	0.9% Normal saline/ Hartmann's/ plasmalyte/ colloid/ 0.45 saline + dextrose/ 0.18 saline + dextrose/ other (please specify)
Further administration of intravenous fluid (IVF) in the first 3 days of admission? ( Appendix B )	Yes/no
Bag 2	
Date of administration	Date (dd/mm/yyyy)
Time of administration	Time (24-hour)

Volume administered	Volume (ml)
Time fluid is administered	Time (hours)
Type of fluid	0.9% Normal saline/ Hartmann's/ plasmalyte/ colloid/ other (please specify)
Further administration of intravenous fluid (IVF) in the first 2 days of admission?	Yes/no
Documented fluid review after 12 hours ( $\pm$ 4 hours)	Yes/no
Documented fluid review after 24 hours ( $\pm$ 4 hours)	Yes/no
Documented fluid review after 48 hours ( $\pm$ 4 hours)	Yes/no
Documented fluid review after 72 hours ( $\pm$ 4 hours)	Yes/no
Early Nutritional support	
On admission patient kept nil by mouth (NBM)	Yes/no

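### 30-day outcomes after transfer to a non-participating hospital have no stated source and no 'unknown' code, and transfers after 72 hours are not recorded, so secondary outcomes may be under-recorded in sicker patients

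*Protocol*

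**What the plan says.** **Hand-over.** Section 6.4 applies "In the event of patient transfer to another participating site". The mechanism is contact between two study leads: "The hospital lead will then liaise with the hospital lead at the receiving site to ensure continuity of data collection". No rule is given for any other receiving hospital.

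**Participation.** Section 5.1 invites hospitals and does not guarantee full coverage: "PANORAMA welcomes the participation of any publicly funded secondary or tertiary hospital in AoNZ". Section 10.2 lets the writing committee drop a unit whose data are substantially incomplete.

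**Source of outcomes.** Section 5.6 specifies chart review at 30 days. Section 6.1 says "follow-up data will be collected from routine clinical notes; No phone calls will be made". Section 5.3 adds "Individuals working at other centres, and those without access to patient clinical data, will not be involved in data collection".

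**Fields in 5.5.** Dialysis, ventilation, inotropes and local complications are Yes/no. Death is a date or 'not dead', and discharge is a date or 'not discharged'. None of these lists 'unknown' or 'transferred out'. The transfer item reads "Patient transferred to a different hospital in the first 72 hours". It is followed by location and reason, and by a date item whose listed answers are Yes/No.

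**Use.** Section 4.2 makes organ support, intervention for a complication, and being alive and discharged at 30 days secondary outcomes. Two secondary aims in section 2 relate QPI compliance to clinical outcomes, stratified by severity.

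**The concern.** Transfer is tracked for three days, while outcomes are collected for thirty. If a patient moves to a hospital with no study lead, the protocol names no one to find out what happened next and gives the form no way to say that it is not known. The sending site is left with 'No', 'not dead' or a blank. Section 10.2 removes collaborators from authorship when their hospital's data are incomplete, which discourages blanks.

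The listed reasons for transfer are severe disease, ERCP and intervention for a local complication. Any loss therefore falls on the patients most likely to have the secondary outcomes. Persistent organ failure also defines severe disease in Appendix A (i), so lost follow-up could place a patient in the wrong severity stratum. An analysis plan written later cannot repair this, because a false 'No' looks the same as a true one and a transfer after 72 hours leaves no field behind it.

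**Working it through.** The protocol gives no transfer rate, participation rate or sample size, so there is no figure to reproduce. The check has two parts.

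**1. The passages side by side**

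| Situation | Outcome route stated? | Transfer visible in the data? |
|---|---|---|
| Transfer within 72 h, participating site | Yes (6.4) | Yes (5.5) |
| Transfer within 72 h, other hospital | No | Yes, with location and reason but no usable date |
| Transfer after 72 h, participating site | Yes (6.4) | No |
| Transfer after 72 h, other hospital | No | No |

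The last row is the worst case: no route to the outcome and no trace of the transfer.

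**2. How large the bias could be, and which way it could run**

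All inputs here are assumptions, except that the range of p is taken from the 20-40% mortality quoted for severe disease in section 1.

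- p: true event risk, the same in compliant and non-compliant patients (true odds ratio 1)
- t: share of a group that is transferred
- q: share of transfers that go to non-participating hospitals
- m: share of lost outcomes entered as 'No' (the rest are missing and dropped)

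Observed risk = p(1 − tq) / (1 − tq(1 − m)).

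Example with p = 0.30, q = 0.3, m = 1:
- compliant, t = 0.4: 0.30 × (1 − 0.12) = 0.264
- non-compliant, t = 0.1: 0.30 × (1 − 0.03) = 0.291
- odds ratio = (0.264/0.736) / (0.291/0.709) = 0.87

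Observed odds ratios for p = 0.30, m = 1:

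| Transferred: compliant / non-compliant | q = 0.1 | q = 0.3 | q = 0.5 |
|---|---|---|---|
| 40% / 10% | 0.96 | 0.87 | 0.79 |
| 40% / 40% | 1.00 | 1.00 | 1.00 |
| 10% / 40% | 1.04 | 1.14 | 1.26 |

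- With q = 0.3 and p from 0.20 to 0.40, the first row runs from 0.89 to 0.86 and the last from 1.13 to 1.17.
- If half the lost outcomes are entered as 'No' (m = 0.5, p = 0.30, q = 0.3), the first row gives 0.93 and the last 1.07.
- If q = 0, or if m = 0 with equal risk in transferred patients, the odds ratio is 1.00.

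**Does coding as missing cure it?** Not fully, if transferred patients are at higher risk. Assume a risk of 0.40 if transferred and 0.20 if not, with t = 0.4 and 0.1, and q = 0.3.
- True risks: 0.4 × 0.40 + 0.6 × 0.20 = 0.28 and 0.1 × 0.40 + 0.9 × 0.20 = 0.22; odds ratio 1.38.
- Lost outcomes entered as 'No': 0.4 × 0.7 × 0.40 + 0.6 × 0.20 = 0.232 and 0.1 × 0.7 × 0.40 + 0.9 × 0.20 = 0.208; odds ratio 1.15.
- Lost outcomes missing: 0.232/0.88 = 0.264 and 0.208/0.97 = 0.214; odds ratio 1.31.

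Coding as missing recovers most of the distortion, but not all of it.

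**The case against.** A reader might infer that unseen events will be recorded as 'No' and that the loss favours compliance. The documents support neither.

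- **Entry as 'No' is not stated.** Nothing makes the fields mandatory, and sections 8 and 10.2 both foresee missing data. This stands: the risk is that events may be entered as negatives. But imputation is optional and acts only on values recognised as missing, and uneven handling across sites is itself a fault.
- **Direction is not established.** QPI 6 in Table 1 concerns discussion with a specialist service, not transfer. Bias towards compliance needs discussed patients to be transferred to non-participating hospitals more often. That is plausible for QPI 6 and not shown for the other 11 domains or for overall compliance. For 'alive and discharged', a sending site could enter its own discharge date (a false success) or 'not discharged' (a false failure). This stands.
- **Early transfers can be found.** The location field allows transfers within 72 hours to non-participating hospitals to be flagged and set to missing. This stands, and it limits the claim that transfers cannot be identified to those after 72 hours.
- **Outside records are not forbidden.** Sections 5.3 and 6.1 do not bar sending-site staff from discharge summaries or shared records already open to them. This stands; the protocol does not say that they should use them.
- **The loss may be nil.** All public hospitals are eligible, and if every receiving hospital takes part nothing is lost. This is correct, but participation is not guaranteed.

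**Conclusion.** The gap is real and limited. The protocol gives no route to 30-day outcomes after transfer to a non-participating or later removed hospital, no code for an outcome that could not be ascertained, and no record of transfers after 72 hours. Events in transferred patients may therefore be under-recorded, and after 72 hours the affected patients cannot be identified.

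The primary outcome, QPI compliance, uses no 30-day outcome and is unaffected. The secondary clinical outcomes and the comparisons of compliant with non-compliant care are exposed, and possibly the severity strata.

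The size is unknown. Under the assumed transfer rates, with every lost outcome entered as 'No' and p = 0.30, a true odds ratio of 1 appears as anything from 0.79 to 1.26. The sign depends on which group is transferred more often. The size depends on how many receiving hospitals stay outside the study and how sites fill the form. The change is worth making because it is cheap and must be made before data are collected.

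**What to change.** **Section 5.5.** Record any transfer up to day 30, with a true date field and the receiving hospital. Add 'transferred out - not ascertained' to each 30-day organ-support, complication, intervention, discharge and vital-status field.

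**Section 6.4.** State that, for a receiving hospital that does not take part or is later removed, the sending lead completes the day-30 fields from discharge summaries or shared records already accessible to them, and otherwise uses the new code.

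**Analysis.** Treat the code as missing, never as 'No', and report its frequency by QPI 6 status.

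**Cost.** A few REDCap response options, a longer window for one item and a short addition to 6.4. Some outcomes that would have been entered as 'No' become missing, with a small loss of precision. Coding as missing reduces the bias but may not remove it where transferred patients are at higher risk; reporting the frequency lets readers judge what remains.

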## 6.5. Maori Health Directorate

The Whangārei Hospital Māori Health Directorate and [name] offered guidance and advice in the conceptualisation stages of this project. Previous research has shown that Māori have significantly higher rates of AP and diabetes mellitus following ap than non-Māori. In a study of Northland hospitals, a retrospective study found no significant differences in severe AP, mortality or intensive care admission between Māori and non-Māori (20). However, its retrospective design and modest sample size limits the validity of the conclusions, warranting further investigation of this phenomenon.

Ethnicity data will be collected and its impact on the outcomes investigated. If a disparity in outcomes is found it will be imperative that this is reported with the aim of improving outcomes for our Māori patients. Findings (including any preliminary findings) of the study will be discussed early with local research offices who will have systems in place for dissemination to those relevant stakeholders for discussion and action.

## 7. Funding

Application for funding will be made to the Auckland Medical Research foundation.

## 8. Statistical analysis

The study will be reported in accordance with the Strengthening the Reporting of Observational Studies in Epidemiology (STROBE) statement (21). The primary analyses will be descriptive assessments of adherence to unambiguous recommendation in the selected domains of early AP management. Descriptive analysis will be performed where normal continuous variables will be compared via student's t test, and non-normal continuous variables will be compared via Mann-Whitney U test; if >2 categories a one-way ANOVA or Kruskal-Wallis test will be used for normal and non-normal variables respectively, Chi-square tests will be used to detect differences between categorical variables. All analyses will be conducted under a two-tailed hypothesis. Multiple imputation may be used in the case of missing data.

Secondary analyses will evaluate the differences in results according to the hospital. Risk-adjusted funnel plots will be produced to test the performance of individual, anonymised centres for normal rates of primary and selected secondary outcomes. Funnel plots' Y-axes will demonstrate QPI of a management domain and X-axis will show the number of patients admitted in each hospital. Furthermore, differences in clinical outcomes between patients that are managed according to best available evidence (QPI) and those that were not will be explored through mixed effects multivariable logistic models. These models will use the patient at the fixed effect level 1 and the hospital as the random effect level 2 (using the R lmer package) will be performed. A one level, fixed effect binary logistic regression model using a pooled dataset from 5 multiply imputed datasets will also be used in the event of substantial missing data.

Variable selection will be based on statistically significant univariable analysis and those variables deemed clinically significant. Fixed, forced entry will be used to adjust the main outcome measure, The effect of interaction, and sequential removal of non-significant variables will be assessed using changes in Akaike information criteria for multilevel models, and p-values for multiple imputed fixed models.

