All hospital leads will also be required to complete a hospital-survey which assess hospital-related variables (*Appendix C*).

Data collection will occur at two timepoints. The first time point will be within or at 48 hours of admission to hospital and secondly at 30-days follow-up following admission to the emergency department .

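### Section 8 names only independence-based tests for its descriptive comparisons and a one-level model for missing data, so comparisons by hospital-level or unevenly spread factors would be anti-conservative

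*Protocol*

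**What the plan says.** The first paragraph of Section 8 (Protocol) describes the primary analysis: "The primary analyses will be descriptive assessments of adherence to unambiguous recommendation in the selected domains of early AP management". The same paragraph lists Student's t, Mann-Whitney, one-way ANOVA and Kruskal-Wallis tests for continuous variables and adds "Chi-square tests will be used to detect differences between categorical variables", with "All analyses will be conducted under a two-tailed hypothesis". It does not mention hospital, names no grouping variable for the tests, and gives no interval for adherence.

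The second paragraph does allow for hospital. It states "Secondary analyses will evaluate the differences in results according to the hospital", plans risk-adjusted funnel plots by centre, and relates compliance to clinical outcomes with mixed logistic models: "These models will use the patient at the fixed effect level 1 and the hospital as the random effect level 2". It then provides, for substantial missing data, that "A one level, fixed effect binary logistic regression model using a pooled dataset from 5 multiply imputed datasets will also be used". That model has no hospital term.

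The third paragraph chooses model variables partly by univariable significance. In the imputed-data models it judges variable removal by p-values.

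Two other places bear on the point. Section 5.3 says "All hospital leads will also be required to complete a hospital-survey which assess hospital-related variables"; Appendix C lists these (beds, ICU, HDU, interventional radiology, endoscopy, ERCP, EUS). Section 6.5 says "Ethnicity data will be collected and its impact on the outcomes investigated".

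**The concern.** Section 4.2 makes variation in compliance between hospitals an outcome, so the protocol itself expects patients in one hospital to resemble each other. The tests in the first paragraph take each patient as a separate piece of information. For a factor that every patient in a hospital shares, such as ERCP availability, the information comes mainly from the number of hospitals, and a patient-level test overstates it. The same happens in weaker form for a patient characteristic whose frequency differs between hospitals.

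At stake are three things:

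- **Group comparisons.** Chance differences between hospitals could be read as effects of hospital facilities or of ethnicity.
- **Model building.** If these simple tests do the univariable screening, understated p-values help decide what enters the models. In the one-level imputed-data model, p-values that ignore hospital also decide what stays.
- **Precision.** A simple binomial interval around national adherence would look tighter than the data allow.

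Section 8 is also not consistent with itself: the complete-data outcome models allow for hospital, and the imputed-data model drops it.

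**Working it through.** The protocol states no sample size, alpha, ICC, number of hospitals or interval width, so there is no figure of its own to reproduce. The sizes below are scenarios.

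**Inputs**

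- From the protocol: incidence 58 per 100,000 adults per year (Section 1); 3 months of recruitment (Section 10.1); two-sided tests (Section 8).
- Assumed: 4 million adults; 20 participating hospitals; hospital-size CV 0.6; alpha 0.05; ICC of adherence 0.01 to 0.10.
- Cohort size: 58/100,000 × 4,000,000 × 3/12 = 580, or 580/20 = 29 per hospital, taken as about 30. With 3.5 to 4.3 million adults the cohort is about 510 to 620.

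**1. Hospital-level factor, half the hospitals in each group**

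Design effect DE = 1 + [(1 + CV²)m − 1] × ICC. With m = 30 and CV = 0.6, (1.36 × 30) − 1 = 39.8. The actual error of a nominal 5% test is 2 × [1 − Φ(1.96/√DE)].

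| ICC | DE | Formula | Simulated, 20 × 30 | Simulated, 20 × 29 |
|---|---|---|---|---|
| 0.01 | 1.40 | 9.7% | 9.0% | 9.2% |
| 0.05 | 2.99 | 25.7% | 25.9% | 24.7% |
| 0.10 | 4.98 | 38.0% | 37.6% | 36.9% |

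The two simulations were run separately, with beta-distributed hospital adherence (mean 50% and 60%) and no true effect. A cluster-robust test on the 20 × 30 data gave 5.4%, 6.5% and 7.2%. With equal hospital sizes (20 × 29) the simple test gave 8.1%, 20.9% and 31.8%.

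The result depends strongly on the inputs. By the equal-size formula it runs from 6.0% (10 patients per hospital, ICC 0.01) to 45.6% (60 patients, ICC 0.10). A rate of 25% needs DE = 2.90, for example ICC 0.05 with 40 patients per hospital or 0.10 with 20.

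**2. Patient-level factor**

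Approximately, DE = 1 + 39.8 × ICC(outcome) × ICC(factor). At outcome ICC 0.05:

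| ICC of factor | DE | Formula | Simulated |
|---|---|---|---|
| 0 | 1.00 | 5.0% | 5.2% |
| 0.05 | 1.10 | 6.2% | 5.8% |
| 0.15 | 1.30 | 8.5% | 7.8% |
| 0.30 | 1.60 | 12.1% | 10.2% |

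An evenly spread factor shows no inflation. At outcome ICC 0.10, factor ICCs of 0.15 to 0.30 gave 11% to 17%.

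**3. Simple binomial interval for national adherence**

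If hospitals are viewed as a sample from a large population, DE = 2.99 at ICC 0.05 gives coverage of about 74% (simulated 75%; 90% at ICC 0.01 and 62% at ICC 0.10). The cluster-robust interval covered about 94%.

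The target, however, is the finite set of public hospitals. DE splits into a within-hospital part, 1 − 0.05 = 0.95, and a between-hospital part, 0.05 × 40.8 = 2.04. If a share f of hospitals takes part, DE is roughly 0.95 + (1 − f) × 2.04:

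- f = 1: 0.95, no loss of coverage
- f = 0.8: 1.36, coverage about 91%
- f = 0.5: 1.97, coverage about 84%

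**The case against.** The strongest reply is that the protocol never specifies the comparisons that would suffer most. Appendix C only collects hospital characteristics, no aim compares adherence by them, and the tests have no named grouping variable. Nor is an interval for national adherence specified. A reader might infer that the primary analysis has a false-positive rate of about 25%, or that its intervals are too narrow as planned. The document supports neither: the rate belongs to one assumed scenario for a comparison that is possible but not planned, and the interval problem arises only if a simple one is calculated.

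Other parts of the reply also stand. The planned models of clinical outcome by compliance already include hospital. Funnel plots by centre address variation between hospitals. A simple test of whether hospitals differ from each other is valid, because independence within hospital is then the right null. Evenly spread patient-level factors are unaffected. If nearly all public hospitals take part, the national proportion is close to a census figure.

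The reply does not remove the point. This is not detail left to an analysis plan: Section 8 names the methods, and no other simple test is named for hospital-survey variables, ethnicity or univariable screening. The one-level model is explicit. Full participation cannot be assumed, since centres opt in (Section 5.1) and units with substantially incomplete data may be excluded (Section 10.2).

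**Conclusion.** The point holds in conditional form. Section 8 is firm about tests that ignore hospital and about a one-level model for imputed data, in a study that expects hospitals to differ and allows for this in its main outcome models. The harm is confined to hospital-level factors, factors unevenly spread across hospitals (ethnicity may be one), univariable screening, the imputed-data model, and any simple interval for national adherence.

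The inflation could be modest or large for hospital-level factors. It is absent to moderate for patient-level ones, and for the interval it depends on participation. Every figure rests on an assumed ICC, hospital count and cluster size. The direction of the error does not depend on those values, provided adherence or outcome varies between hospitals. The change is worth making before analysis because it is cheap.

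**What to change.** Amend Section 8 as follows:

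- For comparisons of adherence or outcomes by hospital-survey variables or ethnicity, and for univariable screening, use a mixed model with a hospital random intercept, cluster-robust standard errors, or a Rao-Scott chi-square test.
- Give any confidence interval for adherence, overall or by domain, by a method that allows for clustering by hospital. If participation is nearly complete, say whether the participating hospitals are treated as the whole target population.
- Keep the hospital random effect, or cluster-robust errors, in the model fitted to the multiply imputed data.
- Keep the simple tests for comparing hospitals with each other.

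This is a wording change plus a little analysis work. No new data are needed: records are collected by site and the mixed model is already planned. The price is wider intervals and fewer significant differences, mainly for hospital-level factors.
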